1.2.2. Randomization Methodology

Randomization was not performed as this is a single treatment, open-label study.

1.2.3. Unblinding

Unblinding is not applicable to this open-label study.

1.2.4. Stopping Rules

See the study Protocol Section 3.5 for stopping rules for this study.

1.2.5. Study Procedures

The schedule of events (SOE) to be performed is provided in the study Protocol Section 6.1.

1.2.6. Study Endpoints

1.2.6.1. Primary Efficacy Endpoint

VOE-CR, defined as complete resolution of vaso-occlusive events (VOEs), between 6 months and 18 months after drug product infusion.

1.2.6.2. Key Secondary Efficacy Endpoints

- sVOE-CR, defined as complete resolution of severe vaso-occlusive events (sVOEs), between 6 months and 18 months after drug product infusion.
- Globin Response, defined as meeting the following criteria for a continuous period of at least 6 months after drug product infusion:
 - a. Weighted average HbA^{T87Q} percentage of non-transfused total Hb¹ $\geq 30\%$
AND
 - b. Weighted average non-transfused total Hb¹ increase of ≥ 3 g/dL compared to baseline total Hb² OR weighted average non-transfused total Hb¹ ≥ 10 g/dL

¹ Non-transfused total Hb is the total g/dL of HbS + HbF + HbA₂ + HbA^{T87Q}. For subjects with a β^+ allele, HbA will also be included in the calculation of “non-transfused total Hb” only for samples taken ≥ 60 days after last pRBC transfusion.

² Baseline total Hb is defined as follows:

The average of the 2 most recent Hb assessments made at or prior to the Screening evaluation, which meet the following criteria:

- (i) Assessments must be separated by at least 1 month from each other.
- (ii) Assessments must have been drawn no earlier than 24 months prior to informed consent and may include the Hb result from Screening.
- (iii) The subject will not have received a pRBC transfusion within 3 months prior to each Hb assessment.

For subjects who are on chronic, recurrent transfusions, and do not have 2 Hb assessments which meet criteria (i), (ii), and (iii), the following criteria can be used: 2 Hb values which meet criteria (i) and (iii) that are found within 24 months prior to the start of a regular transfusion program.

1.2.6.3. Additional Secondary Efficacy Endpoints

Clinical and Disease Evaluation Endpoints:

- Change in the annualized number of VOEs in the 24 months after drug product infusion compared to the 24 months prior to Informed Consent.
- Change in the annualized number of severe VOEs in the 24 months after drug product infusion compared to the 24 months prior to Informed Consent.

- VOE-CR24, defined as complete resolution of VOEs between 6 months and 24 months after drug product infusion
- sVOE-CR24, defined as complete resolution of severe VOEs between 6 months and 24 months after drug product infusion
- sVOE-75, defined as at least a 75% reduction in annualized severe VOEs in the 24 months after drug product infusion compared to the 24 months prior to Informed Consent

Characterization of Globin Response:

- Proportion of subjects who meet the definition of Globin Response at Month 24
- Duration of Globin Response

Hematologic Endpoints:

- Weighted average for the following at Month 6, 12, 18, and 24:
 - non-transfused total Hb¹
 - HbS percentage of non-transfused total Hb¹
 - HbS percentage of non-transfused total Hb¹ $\leq 70\%$, $\leq 60\%$, $\leq 50\%$
 - HbA^{T87Q} percentage of non-transfused total Hb¹
 - non-HbS³ percentage of non-transfused total Hb¹
- Assessment of the following over time:
 - non-transfused total Hb¹
 - HbS percentage of non-transfused total Hb¹
 - HbA^{T87Q} percentage of non-transfused total Hb¹
 - non-HbS³ percentage of non-transfused total Hb¹

¹Non-transfused total Hb is the total g/dL of HbS + HbF + HbA₂ + HbA^{T87Q}. For subjects with a β^+ allele, HbA will also be included in the calculation of “non-transfused total Hb” only for samples taken ≥ 60 days after last pRBC transfusion.

³Non-HbS is the total g/dL of HbF + HbA₂ + HbA^{T87Q}. For subjects with a β^+ allele, HbA will also be included in the calculation of “non-HbS” only for samples taken ≥ 60 days after last pRBC transfusion.

- Change from baseline in hemolysis markers, including absolute reticulocyte count, % reticulocytes/erythrocytes, total bilirubin, haptoglobin, and lactate dehydrogenase
- Change from baseline in markers of iron stores including ferritin, liver iron content, and if assessed at baseline, cardiac iron content
- Change from baseline in annualized frequency and volume of packed red blood cell (pRBC) transfusions between 6 months and 24 months after drug product infusion
- Change from baseline in markers of stress erythropoiesis, including erythropoietin and serum transferrin receptor

SCD Burden and Chronic Complications Assessments:

- Change from baseline in renal function as measured by eGFR

- Change from baseline in cardiac-pulmonary function via echocardiogram (tricuspid regurgitant jet velocity [TRJV], LVEF) and pulmonary function tests
- Change from baseline in meters walked during 6-minute walk test

Hospitalizations and Quality of Life:

- Change from baseline in annualized VOE-related hospital admissions and days
- Change from baseline in patient-reported quality of life, as measured by Patient Reported Outcomes Measurement Information System (PROMIS)

1.2.6.4. Exploratory Efficacy Endpoints

- Change from baseline in cerebral vasculature and prior brain parenchymal injury evaluation at Month 12 and Month 24 (as measured by cerebral magnetic resonance angiography [MRA]/magnetic resonance imaging [MRI] in all subjects, and transcranial Doppler [TCD] for subjects \leq 16 years old at Informed Consent)
- Change from baseline in bone mineral density (BMD) evaluation using dual x-ray absorptiometry (DXA) at Month 24
- Change from baseline in brain natriuretic peptide (BNP)
- Change from baseline in Patient Reported Outcome (PRO) measures including:
 - Overall health: EuroQol-5D (EQ-5D-3L or EQ-5D-Y)
 - Work productivity, as measured by the Work Productivity and Activity Impairment Questionnaire-General Health (WPAI-GH or Caregiver WPAI-GH)
 - Cognitive function as measured by PROMIS Short Form 6a
- Evaluation of chronic pain using AAPT
- Change from baseline in pain medication use
- Exploratory assays to assess change from baseline in sickle cell characteristics and bone marrow pathophysiology

1.2.6.5. Pharmacodynamic Endpoints

- Vector copy number (VCN) in peripheral blood over time
- Expression of β^{A-T87Q} -globin, β^S -globin, and other β -like globins in peripheral blood over time

Additional methods may be used to evaluate pharmacodynamics (PD).

1.2.6.6. Safety Endpoints

Safety will be evaluated by the following:

- Safety and tolerability of plerixafor for mobilization
- Success and kinetics of HSC engraftment
- Transplant-related mortality through 100 days post-drug product infusion and through 365 days post-drug product infusion

- Detection of vector-derived replication competent lentivirus (RCL) in any subject
- The number of subjects with insertional oncogenesis (myelodysplasia, leukemia, lymphoma, etc.)
- The number of subjects with persistent oligoclonality
- Frequency and severity of AEs/SAEs
- Laboratory parameters over time, including the following immunology tests: Screening for irregular antibodies, lymphocyte subpopulation evaluation (CD3, CD4, CD8, CD19, CD16/CD56)
- Incidence of acute and/or chronic graft-versus-host disease (GVHD)
- Other safety labs over time: chemistries, LFTs (AST, ALT, ALP, GGT, bilirubin [total and direct]), hematology, coagulation parameters
- Hormonal testing over time: estradiol (females only); total testosterone (males only) TSH, free T3 (triiodothyronine), free T4 (thyroxine), cortisol, ACTH, FSH, LH (all subjects)
- Change from baseline in methemoglobin concentration at Month 12 and Month 24
- Number of subjects with presence of a chromosomal abnormality or genetic mutation associated with hematologic malignancies over time

2. SUBJECT POPULATION

2.1. Population Definitions

The populations for evaluating efficacy, safety, or pharmacodynamic analyses are listed and defined in [Table 2](#). Study endpoints and their corresponding analysis populations are listed in [Table 3](#). Additional supportive or supplementary analysis might be performed in other analysis populations or groups.

Table 2. Population Definitions

Population	Definition
Intent-to-Treat (ITT) Population	All subjects who initiate any study procedures, beginning with stem cell collection procedures (mobilization/apheresis or bone marrow harvest)
Transplant Population (TP)	All subjects who receive drug product
Successful Engraftment Population (SEP)	A subset of TP subjects who, following busulfan myeloablation and drug product infusion, successfully engraft with drug product, defined as 3 consecutive absolute neutrophil count (ANC) $\geq 0.5 \times 10^9/L$ laboratory values obtained on different days after the initial post-infusion nadir by Day 43
Transplant Population for VOE (TPVOE)	A subset of TP subjects who have at least 4 protocol VOEs in the 24 months prior to Informed Consent

Table 3. Endpoints and the Corresponding Analysis Population

Endpoints	Analysis Population ¹
Demographics and baseline characteristics	ITT
Efficacy endpoints	
Primary endpoint: VOE-CR	Group C subjects in TPVOE
Key secondary endpoint: sVOE-CR	Group C subjects in TPVOE
Key secondary endpoint: Globin Response	Group C subjects in TP
Other secondary endpoints:	
Globin Response at Month 24, Duration of Globin Response	Group C subjects who achieved Globin Response
sVOE-CR24, VOE-CR24, sVOE-75, Change in annualized number of sVOEs	Group C subjects in TPVOE
Change in annualized pRBC transfusions	Group C subjects in TP
Change in annualized VOE-related hospitalizations	TP
Change in annualized number of VOEs	TPVOE
Remaining other secondary endpoints	TP
Exploratory endpoints	TP
Pharmacodynamic endpoints	TP
Safety endpoints ²	ITT or TP

Note: selected endpoints may be repeated in SEP as supportive, if different than TP.

¹ Additional supportive or supplementary analysis may be performed in other analysis population or groups.

² Selected safety endpoints, such as treatment-emergent adverse events, will be based on subjects in TP.

2.2. Protocol Deviations

All protocol deviations will be presented in a listing. The number and percentage of all major deviations in ITT population will be summarized by group. Protocol deviations due to COVID-19 will also be presented in a listing and summarized in a table.

Categorization of protocol deviations will be determined by a review of the protocol deviation data collected on the case report form (CRF). Determination of major/minor and categorization of each protocol deviation type will be made prior to database lock.

3. GENERAL STATISTICAL METHODS

3.1. Sample Size Justification

The sample sizes for Groups A and B are not determined by formal statistical methods.

Approximately 41 subjects will be enrolled in Group C with approximately 35 subjects meeting the severe VOE criteria as defined in Inclusion Criterion #3.1.

- For the primary endpoint, VOE-CR: assuming 80% of Group C subjects in the TPVOE will meet the primary efficacy endpoint, 35 subjects will provide more than 99% power to reject the null hypothesis of 40% at 1-sided alpha of 0.025, using the Exact Test per EAST® (Version 6). The success criterion is 60% (21 out of 35) of subjects meeting the primary efficacy endpoint, if exactly 35 subjects with at least 4 VOEs in the 24 months prior to ICF are enrolled and receive drug product in Group C.
- For the key secondary endpoint, sVOE-CR: assuming 85% of Group C subjects in the TPVOE will meet the primary efficacy endpoint under the alternative hypothesis, 35 subjects will provide more than 99% power to reject the null hypothesis of 50% at 1-sided alpha of 0.025, using the Exact Test per EAST® (Version 6). The success criterion is 69% (24 out of 35) of subjects meeting the key secondary endpoint, if exactly 35 subjects who have at least 4 VOEs in the 24 months prior to ICF are enrolled and received drug product in Group C.
- For the key secondary endpoint, Globin Response: assuming 70% of Group C subjects in the TP will meet the key secondary efficacy endpoint under the alternative hypothesis, 41 subjects will provide approximately 96% power to reject the null hypothesis of 40% at 1-sided alpha of 0.025, using the Exact Test per EAST® (Version 6). The success criterion is 59% (24 out of 41) of subjects meeting the key secondary efficacy endpoint, if exactly 41 subjects are enrolled and received drug product in Group C.

3.2. General Methods

All outputs will be incorporated into Adobe Acrobat portable document format (PDF) files or rich text files (RTF), sorted, and labelled according to the International Council for Harmonization (ICH) recommendations, and formatted to the appropriate page size(s).

Upon consultation with the Medical Monitor, screen-failed subjects may be allowed for re-screening for eligibility to enter the study with a new subject ID, and the re-screening eligible subjects will be presented by the new subject ID in the study. A listing will be provided for screening failure patients. For re-screened subjects, the listing will include original and new subject ID, original screening and re-screening date and result. The demographic information and the group enrolled (if it is available) will also be provided.

Subjects will be presented by study assignment group. No new Subject ID was assigned for two subjects PPI and PPI who were originally assigned to Group B2 and then were re-assigned to Group C in which both drug product and back-up cells were derived from plerixafor mobilization. These two subjects will be included in Group C for all the analyses.

If a subject in the TP develops a hematologic malignancy during the study, the following rules may apply:

- Tables and figures of efficacy endpoints, including but not limited to Hb fractions via high-performance liquid chromatography (HPLC), VOEs, sVOEs, and peripheral blood VCN, will be based on the data up to the date of diagnosis of the malignancy. For binomial proportion endpoints assessing periods of time [e.g., VOE-CR, sVOE-CR] the subject will be considered a non-responder if evaluable for the endpoint and the hematologic malignancy occurs during the endpoint period. For continuous endpoints (e.g., Hb fractions, PB VCN, annualized number of VOEs) data will be censored after the time of hematologic malignancy.
- All the efficacy endpoints will be included in the listings.
- Safety endpoints will be based on the data through the end of study.

For continuous variables, descriptive statistics such as the number of observations or subjects, mean, standard deviation (SD), median, 25% percentile (Q1) and 75% percentile (Q3) as needed, minimum and maximum values will be presented. Mean, median, Q1, Q3, and 95% confidence intervals (CI) will be rounded to 1 additional decimal place compared to the original data (maximum of 3 decimal places). The SD will be rounded to 2 additional decimal places compared to the original data. Minimum and maximum will be displayed with the same accuracy as the original data. The maximal decimals for SD will be 4.

For categorical variables, summary of the number and percentage within each category of the parameter will be presented. A shift table, for change from baseline, can be provided as appropriate. In the shift table, baseline, the worst value within each visit window post-drug product infusion (if there is more than 1 value), and the worst value during the entire follow-up post-drug product infusion will be presented as needed.

Descriptive summary statistics, as well as 2-sided 95% CI, will be presented on selected parameters, as described in the sections below. The exact CI for proportion will be calculated using Clopper-Pearson exact method.

Longitudinal data (collected serially over time on study) will be presented by appropriate time intervals, such as monthly, quarterly, and so forth, depending on the nature of the data.

For purposes of calculations, a month will be defined as 365.25/12 (30.4375) days and a year as 365.25 days. For reporting by month, calculations will be rounded to the nearest day (i.e., the calculated value at 18 months, 547.9, would be rounded to 548 days; the calculated value at 6 months, 182.6, would be rounded to 183 days).

By-subject listings of data for all completed and discontinued subjects, including screen failures (as appropriate), will be provided. All data listings that contain an evaluation date will contain a relative study day (Rel Day). Pre- and post- drug product infusion study days are numbered relative to the day of drug product infusion, which is designated as Day 1.

3.3. Computing Environment

All planned statistical analyses and data summarizations will be performed using SAS statistical software Version 9.4 or higher, unless otherwise noted.

3.4. Baseline Definitions

For annualized number of endpoints, such as annualized number of VOEs, sVOEs, hospitalizations and pRBC transfusions, baseline will be defined as the annualized number of the corresponding endpoint in the 24 months before Informed Consent.

The definition of baseline total Hb for Globin Response derivation can be found in [Section 1.2.6.2](#). The baseline total Hb values are collected on the eCRF page of Baseline Hemoglobin. A subject will be considered as having no baseline Hb for Globin Response analysis if the subject has 1 or 0 qualifying Hb value from the Baseline Hemoglobin eCRF page.

For liver biopsy, liver MRI, Cardiac MRI, cerebral MRA/MRI, echocardiogram (including LVEF and TRJV), bone mineral density (BMD) and pulmonary function test (PFT), baseline will be defined as the first assessment during screening. If no records at screening, the last assessment prior to Informed Consent will be used.

Unless otherwise specified, for other efficacy, pharmacodynamic, and safety parameters, including shifts in key laboratory parameters, baseline will be defined as the first assessment during screening (which can be identified by the first record on or after date of Informed Consent Form [ICF], but before initiation of stem cell collection).

3.5. Methods of Pooling Data

Data will be presented by group. Efficacy analyses will focus on Group C. However, an overall column will be included as appropriate.

3.6. Adjustments for Covariates

No adjustment for covariates is planned for analysis of this study.

3.7. Multiple Comparisons/Multiplicity

Formal multiplicity adjustment will not be performed. It is expected that most of the secondary and exploratory efficacy endpoints will demonstrate a positive effect of drug product. There are multiple secondary endpoints, which will enable a more complete understanding of the clinical impact of therapy with drug product.

Further, the sample size for this study is modest, therefore consistency of effect in secondary endpoints will add credibility to the results of the primary efficacy analysis.

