7.1. Sample Size Estimation

The sample sizes for Groups A and B were not determined by formal statistical methods. Approximately 41 subjects will be enrolled in Group C, approximately 35 of whom must meet the severe VOE criteria as set forth in Inclusion Criterion #3.1.

Assuming 80% of subjects in Group C who have at least 4 VOEs in the 24 months prior to Informed Consent will meet the primary efficacy endpoint of VOE-CR, 35 subjects will provide more than 99% power to reject the null hypothesis of 40% at 1-sided alpha of 0.025, using the Exact Test per EAST® (Version 6). The success criterion is 60% (21 out of 35) of subjects meeting the primary efficacy endpoint VOE-CR, if exactly 35 subjects with at least 4 VOEs in the 24 months prior to Informed Consent are enrolled and receive drug product in Group C.

Power calculations were also performed for the key secondary efficacy endpoints of sVOE-CR and Globin Response.

Assuming 85% of subjects in Group C with at least 4 VOEs in the 24 months prior to Informed Consent will meet sVOE-CR, 35 subjects will provide more than 99% power to reject the null hypothesis of 50% at 1-sided alpha of 0.025, using the Exact Test per EAST® (Version 6). The success criterion is 69% (24 out of 35) of subjects meeting sVOE-CR, if exactly 35 subjects with at least 4 VOEs in the 24 months prior to Informed Consent are enrolled and receive drug product in Group C.

Assuming 70% of subjects will meet Globin Response, 41 subjects will provide approximately 96% power to reject the null hypothesis of 40% at 1-sided alpha of 0.025, using the Exact Test per EAST® (Version 6). The success criterion is 59% (24 out of 41) of subjects meeting Globin Response, if exactly 41 subjects are enrolled and receive drug product in Group C.

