3.12. Interim Analyses

Interim analyses are planned in support of regulatory submissions. The timing of these analyses and the number of subjects included in each analysis will take into account input from regulatory agencies and applicable regulatory guidance. The rationale for each analysis will be documented outside of this SAP.

The summary tables for interim analysis will be presented based on all data available as of the data cut-off, except for these efficacy endpoints specified below. Only evaluable subjects will be included in summary tables:

- **VOE-CR, sVOE-CR, and change in annualized number of VOEs or sVOEs in the 6 to 18 months post-drug product infusion:** only include Group C subjects in the TPVOE who have or would have at least 18 months follow up post-drug product infusion.
- **sVOE-CR24, VOE-CR24, sVOE-75 and change in annualized number of VOEs or sVOEs in the 24 months post-drug product infusion:** only include Group C subjects in TPVOE who have Month 24 visit or would have at least 24 months follow-up post-drug product infusion.
- **Globin Response (GR):** only include subjects in TP who achieve Globin Response, have or would have at least 18 months follow up post-drug product infusion.
- **Globin Response at Month 24:** only include subjects in TP who achieve Globin Response and either (1) have Month 24 HPLC visit assessment or (2) would have at least 24 months follow up post-drug product infusion.
- **pRBC transfusions, and hospitalizations endpoint:** only include Group C subjects in the TP who have or would have at least 18 months of follow-up post-drug product infusion.

For Group A and B, the analysis population for interim analysis will be based on the same criteria as the criteria of interim analysis for Group C.

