4.4.1. Analysis of Primary Efficacy Endpoint

Analysis for Group C

The primary efficacy endpoint, VOE-CR, is defined as the complete resolution of adjudicated VOE between 6 months and 18 months after drug product infusion. The analysis population can be found in [Table 4](#).

Responders of VOE-CR are subjects who do not have any adjudicated VOEs between 6 months and 18 months (i.e., 183 to 548 days) after drug product infusion.

Non-Responders of VOE-CR are subjects who meet any of the following criteria:

- Has ≥ 1 adjudicated VOE between 6 months and 18 months after drug product infusion. If a subject has an adjudicated VOE that occurs before 183 days but ends after 183 days after drug product infusion, the subject is considered as a non-responder.
- Discontinues from the study on or before 18 months follow-up post-drug product infusion.

The percentage of subjects who achieve VOE-CR will be presented with a 2-sided exact 95% CI using Clopper-Pearson method for the binomial distribution. The success criterion will be at least 21 out of 35 subjects achieving VOE-CR (i.e., rate of VOE-CR $\geq 60\%$), giving a lower bound of the 95% CI greater than 40%, if exactly 35 TPVOE subjects in Group C. If there are fewer than 35 subjects in the analysis population, with the same assumptions such as the null hypothesis as 40% and alternative hypothesis as 80%, the power and success criterion can be found in [Appendix 6.3, Table 13](#).

Supplementary Analyses for Group C

The following Supplementary analyses, but not limited to, will be conducted:

Analysis Population	Supplementary Analysis
TPVOE ^[1]	The primary analysis will be repeated using protocol VOE instead of adjudicated VOE.
TPVOE ^[1]	The primary analysis will be repeated using investigator VOE instead of adjudicated VOE.

Analysis Population	Supplementary Analysis

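### Three endpoints each carry a one-sided 0.025 success rule, but the SAP sets no testing order and names no confirmatory analysis; the chance of at least one false success at a single final look is about 3.4–3.9%

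*SAP*

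**What the plan says.** SAP 3.1 sizes the primary endpoint "assuming 80% of Group C subjects in the TPVOE will meet the primary efficacy endpoint", so that "35 subjects will provide more than 99% power to reject the null hypothesis of 40% at 1-sided alpha of 0.025". SAP 4.4.1 turns this into a pass mark: "The success criterion will be at least 21 out of 35 subjects achieving VOE-CR". The first key secondary endpoint is treated in the same way: "assuming 85% of Group C subjects in the TPVOE" are expected to respond, and "35 subjects will provide more than 99% power to reject the null hypothesis of 50% at 1-sided alpha of 0.025". SAP 4.4.2.1 sets its mark at 24 of 35. Globin Response is tested against 40%, with an assumed rate of 70% and a mark of 24 of 41, which SAP 4.4.2.2 words for the final analysis.

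Protocol 7.1 confirms that the key secondaries were planned formally: "Power calculations were also performed for the key secondary efficacy endpoints of sVOE-CR and Globin Response". Protocol 7.4.4.1 and 7.4.4.2 specify a test for all three endpoints, while 7.4.4.3 makes the other secondary endpoints descriptive.

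On error control, SAP 3.7 says "Formal multiplicity adjustment will not be performed". It gives three reasons: most secondary and exploratory endpoints are expected to show benefit, several endpoints give a fuller picture, and in a modest sample consistent secondary results support the primary. It gives no testing order.

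SAP 3.12 leaves the number, timing and size of interim analyses open and adds "The rationale for each analysis will be documented outside of this SAP". SAP Table 4 defines all three estimands for interim use on evaluable subjects. SAP Table 13 gives cut-offs at the full one-sided 0.025 for populations down to 29 (VOE-CR and sVOE-CR) and 35 (Globin Response). The change log in SAP 5.2 refers to an interim CSR.

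**The concern.** A numeric success criterion invites a claim of success. With three criteria and no order, nothing in the plan prevents sVOE-CR or Globin Response from being declared successful when VOE-CR has failed. The stated 0.025 then describes each test separately, not the set of claims. The reasons in SAP 3.7 do not fill the gap: expecting benefit is not error control, and consistency supports describing the secondaries, not three separate pass marks.

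The second gap is that no analysis is named as the one that decides. Interims are planned and at least one has been reported. A reader of the final report could not tell from the SAP whether the formal test was done then, is done at the end, or both.

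**Working it through.** **Inputs.** Null rates 40%, 50% and 40%; assumed rates 80%, 85% and 70%; sizes 35, 35 and 41; cut-offs 21, 24 and 24 (SAP 3.1, 4.4.1, 4.4.2, Table 13).

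**Step 1: reproduce the plan.** Attained size is P(X ≥ c | n, p0) and power is P(X ≥ c | n, p1), both exact binomial.

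| Endpoint | Rule | Attained size | Size with cut-off one lower | Power |
|---|---|---|---|---|
| VOE-CR | 21/35 | 0.0133 | 0.0300 | 0.9982 |
| sVOE-CR | 24/35 | 0.0205 | 0.0448 | 0.9963 |
| Globin Response | 24/41 | 0.0126 | 0.0270 | 0.9586 |

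The stated cut-offs and powers are correct. Each test is conservative because the counts are discrete.

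**Step 2: any false success at one final look.** SAP Table 14 defines a protocol sVOE as a protocol VOE meeting a further condition. I take the adjudicated events to follow the same structure, so every VOE-CR responder is also an sVOE-CR responder. Under the nulls each subject is then VOE-free (0.40), free of severe VOEs only (0.10) or neither (0.50). From this multinomial with n = 35:

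- P(VOE-CR or sVOE-CR succeeds) = 0.0133 + 0.0205 − 0.0073 (both) = 0.0264. So sVOE-CR succeeds while VOE-CR fails with probability 0.0264 − 0.0133 = 0.0131.
- Adding Globin Response as independent: 1 − (1 − 0.0264)(1 − 0.0126) = 0.0386 from unrounded values.
- With Globin Response correlated with the VOE outcomes (latent correlation 0.5 and 0.9; 200,000 simulated trials): 3.7% and 3.4%.

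The range is therefore about 3.4–3.9%.

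**Step 3: interims, if the rule were applied at each look at full 0.025.** The documents give no schedule, so these looks are assumptions. For VOE-CR alone, the probability of crossing at either of two looks is:

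| Looks | Cut-offs | VOE-CR |
|---|---|---|
| 29, 35 | 18, 21 | 1.9% |
| 30, 35 | 18, 21 | 2.4% |
| 32, 35 | 19, 21 | 2.3% |
| 24, 35 | 15, 21 | 2.7% |
| 20, 35 | 13, 21 | 2.8% |

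The first three schedules use Table 13 cut-offs. The cut-offs at 24 and 20 come from the same exact rule but are not in the SAP. For sVOE-CR the first three schedules give 2.4%, 2.8% and 2.1%. If all three rules were also applied at one interim inside the Table 13 range (29, 30 or 32, then 35; Globin Response at 35, 36 or 38, then 41), any false success would be 4.3–6.1% with the VOE endpoints nested.

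**Step 4: cost of a fixed order.** Without assuming anything about dependence, sVOE-CR power is at least 0.99825 + 0.99632 − 1 = 0.99457. Globin Response power is at least 0.99457 + 0.95864 − 1 = 0.95321. These compare with 0.9963 and 0.9586 unordered. The first test is unchanged, but its power depends on the true VOE-CR rate: P(X ≥ 21 | 35, p) is 92.7% at 70%, 78.9% at 65% and 57.3% at 60%.

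**The case against.** The best defence is that there is one primary endpoint, its attained error at the final look is 1.3%, and SAP 3.7 gives the secondary endpoints a supporting role. No sentence says that a key secondary would be claimed after the primary failed. This stands as a limit on the size of the problem: the primary claim is not inflated at a single look. It does not remove the problem, because two supporting endpoints still have their own tests and pass marks.

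A reader might infer that the same test can be repeated until it passes, and so that the error is well above 2.5%. The documents do not support that. No passage applies a success rule at an interim or provides for stopping early for efficacy. The Globin Response mark is worded for the final analysis, and Table 13 has no cut-off below 29 for the VOE endpoints. For VOE-CR, the late two-look schedules above stay under 2.5%. A reader might also treat the three tests as independent, which gives 1 − (1 − 0.0133)(1 − 0.0205)(1 − 0.0126) = 4.6%, but that contradicts the nesting of severe VOEs within VOEs.

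Two objections to the remedy are sound. The low cost of a fixed order depends on a VOE-CR rate near 80%. And in an open-label study with an interim CSR already written, an order added now is not prospective.

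**Conclusion.** The point holds at a moderate size. Under the plan as written, three formal claims share no order, and the chance of at least one false success at a single final look is about 3.4–3.9%, against 1.3% for the primary alone. This assumes the planned sizes of 35 and 41, all three nulls true, nested VOE endpoints, and a correlation between Globin Response and the VOE outcomes from none to strong. It would shift somewhat at other sizes because the tests are discrete.

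Whether interims add to this cannot be settled from the documents. The defect there is the missing statement of which analysis is confirmatory; the repeated-look figures are illustrations on assumed schedules. The plan should be changed, but the primary test at the final analysis is sound as it stands.

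**What to change.** In SAP 3.7, state a fixed sequence: VOE-CR, then sVOE-CR, then Globin Response, each at one-sided 0.025 and tested only if the one before it succeeds. In SAP 3.12, name the one analysis that carries the formal test, and report every other look as estimates with exact confidence intervals and no success claim. The second statement is needed as well, because an order alone does nothing about repeated looks. Since an interim CSR exists, say whether that analysis was the formal test, and disclose that the order was set after it.

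With both changes, the chance of any false success is at most 2.05%, the largest attained size. No subjects, visits or data are added. At the planned rates sVOE-CR power goes from 99.6% to about 99.5% and Globin Response from 95.9% to about 95.3%. Splitting alpha equally (0.025/3 each) would cost more, leaving 99.5%, 97.1% and 92.1%.

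The real cost is the gate. If the true VOE-CR rate is 70%, 65% or 60%, the first test succeeds with probability 92.7%, 79% or 57%, and a failure there leaves both key secondaries as descriptive results.
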